5.2. Number of Participants

A total of 12 patients will be enrolled so that at least 5 patients with EP and 5 patients with GPP who are inadequate responders (GIS ≥ 2 at Week 12 and based on the investigators' discretion), will continue to use ixekizumab beyond Week 12. Additional enrollment may occur and sample size may be increased, if no GPP or EP patients enter into Period 3 (Maintenance Dosing Period) of the study.

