6.1. Inclusion Criteria

Patients are eligible to be included in the study only if they meet all of the following criteria at screening:

Type of Patient and Disease Characteristics

- [1] Present with GPP or EP based on an investigator-confirmed diagnosis and meet the associated criteria
 - [1a] GPP:
 - Meet the criteria for GPP set by Ministry of Health, Labour and Welfare (MHLW) at screening (Visit 1) and baseline (Week 0; Visit 2) regardless of IL-36 mutation status.
 - [1b] EP:
 - Diagnosed to have BSA $\geq 80\%$ involvement (with inflammatory erythema) at screening (Visit 1) and baseline (Week 0; Visit 2).
- [2] Candidates for phototherapy and/or systemic therapy

Patient Characteristics

- [3] Are at least 20 years of age at the time of screening
 - [3a] male patients:
 - agree to use a reliable method of birth control* during the study
 - [3b] female patients:
 - Are women of childbearing potential who test negative for pregnancy and agree to use a reliable method of birth control* or remain abstinent during the study and for at least 12 weeks following the last dose of investigational product, whichever is longer.
 - or-
 - Are women of non-childbearing potential, defined as:
 - Women who have had surgical sterilization (hysterectomy, bilateral oophorectomy, or tubal ligation);
 - or-
 - Women who are ≥ 60 years of age;
 - or-

Women ≥ 40 and < 60 years of age who have had a cessation of menses for ≥ 12 months and a follicle-stimulating hormone test confirming nonchildbearing potential (≥ 40 mIU/mL).

* Each of the following is considered as highly effective method of birth control:

- oral contraceptives
- condom with spermicide
- intrauterine device
- vasectomized male (with the appropriate post-vasectomy documentation of the absence of sperm in the ejaculate). For female patients in the study, the vasectomized male partner should be the sole partner for that patient.

Informed Consent

- [4] Have given written informed consent approved by Eli Lilly Japan or its designee and the Investigational Review Board/Ethical Review Board (IRB/ERB) governing the site.

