7.2. Method of Treatment Assignment

Patients are assigned to treatment and will receive their assigned treatment as outlined in Section 7.1.

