10.1. Sample Size Determination

A total of 12 patients will be enrolled so that at least 5 patients with EP and 5 patients with GPP who are inadequate responders ($\text{GIS} \geq 2$ at Week 12 and based on investigators' discretion) will continue to use ixekizumab beyond Week 12. Additional enrollment may occur and the sample size may be increased, if no GPP or EP patients enter into Period 3 (Maintenance Dosing Period) of the study.

The sample size is based on the following:

- In the I1F-JE-RHAT (RHAT) study, 5 GPP and 8 EP patients were enrolled. One GPP patient achieved $\text{GIS} = 1$ (resolved) at Week 12 and the other 4 GPP patients achieved $\text{GIS} = 2$ (improved). One EP patient achieved $\text{GIS} = 1$ at Week 12 and 7 EP patients achieved $\text{GIS} = 2$. Although the sample size is very small, based on the result of RHAT study, it is assumed that approximately 5 patients at maximum may not achieve $\text{GIS} = 1$ at Week 12 and may continue ixekizumab Q2W beyond Week 12 based on the investigators' discretion.
- The sample size is determined based on the feasibility in Japan. The prevalence rate of these patients is very low in Japan and it is also difficult to conduct a placebo-controlled study for these severe conditions (Umezawa et al. 2003, Rosenbach et al. 2010).

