## 5.2. Determination of Sample Size

A total of 12 patients will be enrolled so that at least 5 patients with EP and 5 patients with GPP who are inadequate responders ( $\text{GIS} \geq 2$  at Week 12 and based on investigators' discretion) will continue to use ixekizumab beyond Week 12. Additional enrollment may occur and the sample size may be increased, if no GPP or EP patients enter into Period 3 (Maintenance Dosing Period) of the study.

The sample size is based on the following:

- In the I1F-JE-RHAT (RHAT) study, 5 GPP and 8 EP patients were enrolled. One GPP patient achieved  $\text{GIS} = 1$  (resolved) at Week 12 and the other 4 GPP patients achieved  $\text{GIS} = 2$  (improved). One EP patient achieved  $\text{GIS} = 1$  at Week 12 and 7 EP patients achieved  $\text{GIS} = 2$ . Although the sample size is very small, based on the result of RHAT study, it is assumed that approximately 5 patients at maximum may not achieve  $\text{GIS} = 1$  at Week 12 and may continue ixekizumab Q2W beyond Week 12 based on the investigators' discretion.
- The sample size is determined based on the feasibility in Japan. The prevalence rate of these patients is very low in Japan and it is also difficult to conduct a placebo-controlled study for these severe conditions (Umezawa et al. 2003, Rosenbach et al. 2010).

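### The 12 places carry no limit per disease, so 8 patients of one disease would put the target of 5 continuing patients out of reach for the other within the 12

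*Protocol*

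**What the plan says.** The sample size statement in Protocol 5.2 is: "A total of 12 patients will be enrolled so that at least 5 patients with EP and 5 patients with GPP" go on to receive ixekizumab beyond Week 12 as inadequate responders. The Synopsis, Protocol 10.1 and SAP 5.2 say the same.

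The number to enrol is one total, and the number wanted in Period 3 is set for each disease. No section links the two:

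- Inclusion criterion 1 (Protocol 6.1) admits either disease: "Present with GPP or EP based on an investigator-confirmed diagnosis".
- Protocol 7.2 gives a single regimen, with no stratum or limit by disease: "Patients are assigned to treatment and will receive their assigned treatment as outlined in Section 7.1". SAP 5.3 repeats this.
- The clause on enlarging the trial reads: "Additional enrollment may occur and sample size may be increased, if no GPP or EP patients enter into Period 3".

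The size is justified by feasibility and by one prior study: "In the I1F-JE-RHAT (RHAT) study, 5 GPP and 8 EP patients were enrolled". Of these, 4 of 5 GPP and 7 of 8 EP patients were improved but not resolved at Week 12. The primary analysis is reported for GPP and EP separately (Protocol 10.3.3.1, SAP 6.11.1) and is descriptive only.

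**The concern.** Each disease needs 5 patients in Period 3, and 5 + 5 leaves only 2 spare places out of 12. An uneven run of enrolment can use up those places before response plays any part. The trial could then fill all 12 places and fall short of its own figure in one of the two diseases that the regulatory commitment covers. The enlargement clause would not help a disease with 1 to 4 patients in Period 3, because it is worded for none.

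**Working it through.** **Inputs.** Total of 12 and target of 5 + 5 (Protocol 5.2). Prior-study mix of 8 EP to 5 GPP, and non-resolution of 4/5 = 0.80 in GPP and 7/8 = 0.875 in EP (Protocol 10.1, SAP 5.2). The disease mix in this trial is not given, so EP shares of 40% to 70% are assumed.

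**1. The plan's 12.** No formula is given. An expected-value check gives 5/0.80 + 5/0.875 = 6.25 + 5.71 = 11.96, which agrees with 12. Rounding up within each disease gives 7 + 6 = 13. So 12 fits an average outcome and carries almost no margin.

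**2. Splits that can work.** With g GPP and 12 − g EP patients, the target needs g ≥ 5 and 12 − g ≥ 5, so g is 5, 6 or 7. With 8 of one disease, at most 12 − 8 = 4 of the other fit. No response rate enters this step.

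**3. Chance of 8 or more of one disease.** Assume unmanaged first-come accrual, with G ~ Binomial(12, p) and p the GPP share. The chance is P(G ≤ 4) + P(G ≥ 8).

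| EP share | P(GPP ≤ 4) | P(EP ≤ 4) | Total |
|---|---|---|---|
| 40% | 0.057 | 0.438 | 0.50 |
| 50% | 0.194 | 0.194 | 0.39 |
| 60% | 0.438 | 0.057 | 0.50 |
| 8/13 (prior study) | 0.482 | 0.045 | 0.53 |
| 70% | 0.724 | 0.009 | 0.73 |

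The lowest value is at 50:50. With a cap of 7 and all 12 places filled, the chance is 0.

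**4. The enlargement clause.** Read generously, it acts when either disease has no patient in Period 3. Assume every non-resolved patient continues and none drops out. For a given g, the chance that it acts is 1 − (1 − 0.20^g)(1 − 0.125^(12 − g)). Averaged over the binomial split, this is 0.003 at 50:50 and 0.012 at the prior-study mix.

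**5. What a split leaves.** On the assumptions of step 4, the chance of at least 5 continuing in both diseases is P(Bin(g, 0.80) ≥ 5) × P(Bin(12 − g, 0.875) ≥ 5):

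- 6 GPP / 6 EP: 0.655 × 0.833 = 0.55
- 7 GPP / 5 EP: 0.852 × 0.513 = 0.44
- 5 GPP / 7 EP: 0.328 × 0.954 = 0.31

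Averaged over unmanaged splits:

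- 50:50: 0.193 × 0.3125 + 0.226 × 0.546 + 0.193 × 0.437 = 0.27
- Prior-study mix, by the same sum: 0.20

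**The case against.** The strongest reply is that the split is implied. The stated aim allows only 5/7, 6/6 or 7/5, the study is open-label, disease type is confirmed at screening and baseline, and Appendix 3.1.2 gives the sponsor a central recruitment strategy. An eighth patient of one disease would visibly defeat the aim, and the sponsor may be managing this in a document outside the protocol and SAP. This shows intent, and it limits what the probabilities mean. It does not supply a rule in the sections where sites would look for one.

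Two further points stand. The prior study's mix comes from 13 patients, and nothing says that it arose without quotas, so it illustrates a mix and does not estimate one. The consequence is also bounded: there is no test, power or decision rule, and 4 patients in place of 5 make a thinner description, not an invalid analysis.

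A reader might infer that the shortfall would be fixed before any Week 12 result is known. The documents do not support that. It depends on accrual speed, which is not given, and in rare diseases Week 12 results may come before the eighth patient. What can be said is that the limit holds whatever those results are.

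**Conclusion.** The point holds. One total of 12 with a per-disease aim of 5 and no per-disease limit can make that aim unreachable at enrolment, and the enlargement clause almost never applies. The step from 8 enrolled to at most 4 of the other disease is plain arithmetic. The probabilities of 0.39 to 0.73 rest on unmanaged first-come accrual and an assumed mix. They should not be read as this trial's actual risk of falling short.

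A reader might also infer that a fixed split delivers 5 and 5. It does not. At non-resolution rates taken from only 5 and 8 patients, the chance is 0.55 at best within 12, and investigator discretion or dropout would lower it. A limit is still worth having, since 0.31 to 0.55 compares with 0.20 to 0.27 without one, at the same total.

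**What to change.** In the Synopsis, Protocol 5.2 and 10.1, and SAP 5.2, state that no more than 7 patients of either disease are enrolled within the 12, with a target of 6 GPP and 6 EP. In the same places, describe 5 continuing patients per disease as a target and not as something that 12 patients deliver. Reconcile this with the assumption in Protocol 10.1 and SAP 5.2 that about 5 patients at most will continue, which does not say whether it is per disease or in total. The sponsor could also consider letting extra enrolment apply when a disease has fewer than 5 patients in Period 3.

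The text change is a sentence or two and the total stays at 12. The real cost is slower accrual, with some eligible patients of the commoner disease turned away. The cap removes the enrolment-stage problem only if recruitment goes on until the rarer disease fills its places. Stopping at 7 + 4 = 11 would still miss. SAP 6.9 and 6.13.1 mention an IWRS only as a source of dispensing data, so whether it can hold the limit needs checking.

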5.3. End of Study Definition

End of the study is the date of the last visit or last scheduled procedure shown in the Schedule of Activities (Section 2) for the last patient.

5.4. Scientific Rationale for Study Design

This is an open-label, single-arm study to primarily assess the efficacy of ixekizumab Q2W beyond Week 12 in patients with EP and GPP. The absence of a placebo arm is consistent with other studies evaluating efficacy and safety of investigational drugs in these severe forms of Ps. In addition, placebo-controlled studies are not ethical for patients with EP and GPP.

The Induction Dosing Period (Period 2) is based on the dosage and administration which was approved via initial regulatory review. This will be followed by the Maintenance Dosing Period (Period 3), if patients do not show a therapeutic response (GIS ≥ 2 at Week 12 and based on the investigators' discretion).

5.5. Justification for Dose

The dosing schedule for Study RHCV was selected based on the initially approved dosage and administration of ixekizumab, and is designed to evaluate the response of patients with EP and GPP at Week 12 following the administration of ixekizumab at a starting dose of 160 mg followed by 80 mg Q2W up to Week 12. Thereafter, according to the newly approved schedule, patients with an inadequate response will receive a dose of ixekizumab 80 mg Q2W up to and including Week 18, or until they achieve a GIS score of 1.

6. Study Population

Prospective approval of protocol deviations to recruitment and enrollment criteria, also known as protocol waivers or exemptions, are not permitted.

6.1. Inclusion Criteria

Patients are eligible to be included in the study only if they meet all of the following criteria at screening:

Type of Patient and Disease Characteristics

- [1] Present with GPP or EP based on an investigator-confirmed diagnosis and meet the associated criteria
 - [1a] GPP:
 - Meet the criteria for GPP set by Ministry of Health, Labour and Welfare (MHLW) at screening (Visit 1) and baseline (Week 0; Visit 2) regardless of IL-36 mutation status.
 - [1b] EP:
 - Diagnosed to have BSA $\geq 80\%$ involvement (with inflammatory erythema) at screening (Visit 1) and baseline (Week 0; Visit 2).
- [2] Candidates for phototherapy and/or systemic therapy

Patient Characteristics

- [3] Are at least 20 years of age at the time of screening
 - [3a] male patients:
 - agree to use a reliable method of birth control* during the study
 - [3b] female patients:
 - Are women of childbearing potential who test negative for pregnancy and agree to use a reliable method of birth control* or remain abstinent during the study and for at least 12 weeks following the last dose of investigational product, whichever is longer.
 - or-
 - Are women of non-childbearing potential, defined as:
 - Women who have had surgical sterilization (hysterectomy, bilateral oophorectomy, or tubal ligation);
 - or-
 - Women who are ≥ 60 years of age;
 - or-

Women ≥ 40 and < 60 years of age who have had a cessation of menses for ≥ 12 months and a follicle-stimulating hormone test confirming nonchildbearing potential (≥ 40 mIU/mL).

* Each of the following is considered as highly effective method of birth control:

- oral contraceptives
- condom with spermicide
- intrauterine device
- vasectomized male (with the appropriate post-vasectomy documentation of the absence of sperm in the ejaculate). For female patients in the study, the vasectomized male partner should be the sole partner for that patient.

Informed Consent

- [4] Have given written informed consent approved by Eli Lilly Japan or its designee and the Investigational Review Board/Ethical Review Board (IRB/ERB) governing the site.

6.2. Exclusion Criteria

Patients will be excluded from study enrollment if they meet any of the following criteria at screening:

Medical Conditions

- [5] Have any other skin conditions that would affect interpretation of the results (including, but not limited to, scleroderma, eczema, drug-induced psoriasis, guttate psoriasis, parapsoriasis, or cutaneous manifestations of other autoimmune diseases such as systemic lupus erythematosus).
- [6] Have a known allergy or hypersensitivity to any biologic therapy that would pose an unacceptable risk to the patient if participating in this study.
- [7] Had a serious infection (for example, pneumonia, cellulitis), have been hospitalized, or have received IV antibiotics for an infection, within 12 weeks prior to baseline (Week 0; Visit 2), or had a serious bone or joint infection within 24 weeks prior to baseline, or have ever had an infection of an artificial joint, or are immunocompromised to an extent such that participation in the study would pose an unacceptable risk to the patient.
- [8] Have or had an infection typical of an immunocompromised host, and/or that occurs with increased incidence in an immunocompromised host (including, but not limited to, pneumocystis pneumonia (PCP), histoplasmosis, or coccidioidomycosis); or have a known immunodeficiency. Additionally, patients with a positive beta-D-glucan test at screening and a confirmed diagnosis of PCP will be excluded.

- [9] Have or had a herpes zoster or any other clinically apparent varicella-zoster virus infection within 4 weeks of baseline (Week 0; Visit 2).
- [10] Have any other active or recent infection within 4 weeks of baseline (Week 0; Visit 2) that, in the opinion of the investigator, would pose an unacceptable risk to the patients if participating in the study; these patients may be rescreened 4 or more weeks after documented resolution of symptoms.
- [11] Have evidence or suspicion of active or latent tuberculosis (TB).
- [12] Are positive for human immunodeficiency virus serology (HIV; positive for human immunodeficiency virus antibody [HIVAb]).
- [13] Have hepatitis B or test positive for hepatitis B virus (HBV) at screening, defined as:
- Positive for hepatitis B surface antigen (HBsAg+)
- OR
- Positive for hepatitis B core antibody (HBcAb+) in conjunction with positive confirmatory HBV for HBV deoxyribonucleic acid (DNA) test
- OR
- Positive for hepatitis B surface antibody (HBsAb+) and positive confirmatory for HBV DNA.

Note: Patients who are HBcAb+ and/or HBsAb+ and HBV DNA negative may be enrolled in the study. Patients who meet these criteria at screening will be monitored during the study as detailed in protocol Section 9.4.5.4.

- [14] Have hepatitis C or test positive for hepatitis C virus (HCV) at screening, defined as: positive result for hepatitis C antibody and positive confirmatory HCV ribonucleic acid (RNA) test (see protocol Section 9.4.5.5). Patients in sustained virologic response after HCV therapy, and patients who have spontaneously cleared HCV infection (see protocol Section 9.4.5.5) can be included in this study.
- [15] Have clinical laboratory test results at screening that are outside the normal reference range for the population and are considered clinically significant, and/or have any of the following specific abnormalities:
- [15a] Neutrophil count <1500 cells/ μ L
 - [15b] Lymphocyte count <500 cells/ μ L
 - [15c] Platelet count <100,000 cells/ μ L
 - [15d] Aspartate aminotransferase (AST) or alanine aminotransferase (ALT) >2.5 times the upper limit of normal (ULN)
 - [15e] Total white blood cell (WBC) count <3000 cells/ μ L

[15f] Hemoglobin <10.0 g/dL (100.0 g/L)

[15g] Serum creatinine >2.0 mg/dL

[15h] Serum albumin <2.5 g/dL

(Note: The AST and ALT may be repeated once within a week if the initial response exceeds this limit, and the repeat value may be accepted if it meets this criterion.)

[16] Have received systemic nonbiologic Ps therapy or have received phototherapy at the day of baseline (however, see exception below).

- Oral corticosteroids will be permitted, if average daily doses are not greater than 10 mg/day of prednisone or its equivalent.
- All topical treatment will be permitted.
- Methotrexate or oral retinoids will be permitted before and during the study if doses are not greater than that of baseline.
- Cyclosporine and Apremilast will be permitted, if daily doses are not greater than that of baseline

[17] Presence of significant uncontrolled neuropsychiatric disorder, have recent history (within 30 days prior to screening [Visit 1] and any time between screening [Visit 1] and baseline [Visit 2]) of a suicide attempt; or have active suicidal ideation with some intent to act with or without a specific plan (yes to question 4 or 5 on the “Suicidal Ideation” portion of the Columbia-Suicide Severity Rating Scale [C-SSRS]); or are clinically judged by the investigator to be at risk for suicide.

[18] Have had any major surgery within 8 weeks of baseline (Week 0; Visit 2) or will require major surgery during the study that, in the opinion of the investigator in consultation with Lilly, would pose an unacceptable risk to the patient.

[19] Have current or a history of lymphoproliferative disease, or signs or symptoms of lymphoproliferative disease within 5 years of baseline (Week 0; Visit 2); or have active or history of malignant disease within 5 years of baseline (Week 0, Visit 2), except for basal cell carcinoma, squamous cell carcinoma, skin Bowen’s disease, or actinic keratoses that have been treated with no evidence of recurrence in the past 12 weeks, or carcinoma in situ of the cervix, or non-invasive malignant colon polyps that have been removed.

(Note: patients with history of malignancy with no evidence of recurrence or active disease within 5 years of baseline may participate in the study).

[20] Have had fluid overload, myocardial infarction, or new onset ischemic heart disease (e.g., unstable angina), uncompensated heart failure, or in the opinion of the investigator other serious cardiac disease within 12 weeks of baseline (Week 0; Visit 2).

- [21] Have current or a history of inflammatory bowel disease (IBD) (ulcerative colitis and Crohn's disease), or signs or symptoms of IBD at screening (Visit 1) that, in the opinion of the investigator, pose an unacceptable risk to the patient if participating in the study.

Prior/Concomitant Therapy

- [22] Cannot avoid excessive sun exposure or use of tanning booths for at least 4 weeks prior to baseline (Week 0; Visit 2) and during the study.
- [23] Concurrent use of any biologic agent during this clinical study.
- [24] Have previously received ixekizumab treatment.
- [25] Have previously completed or withdrawn from this study.
- [26] Had a live vaccination within 12 weeks prior to baseline (Week 0; Visit 2), intend to have a live vaccination during the course of the study or within 12 months of completing treatment in this study, or have participated in a vaccine clinical study within 12 weeks prior to baseline. Investigators should review the vaccination status of their patients and follow Japan guidelines for adult vaccination with nonlive vaccines intended to prevent infectious disease prior to therapy.
- (Note: Killed/inactive or subunit vaccines are expected to be safe; however, their efficacy with ixekizumab treatment is unknown.)
- [27] Had a vaccination with Bacillus Calmette-Guerin (BCG) within 12 months prior to baseline (Week 0; Visit 2) or intend to have this vaccination with BCG during the course of the study, or within 12 months of completing treatment in this study.

Prior/Concurrent Clinical Trial Experience

- [28] Are currently enrolled in any other clinical study involving an investigational product or any other type of medical research judged not to be scientifically or medically compatible with this study.
- [29] Have participated in any other clinical study during this clinical study.

Other Exclusions

- [30] Have any other condition that precludes the patient from following and completing the protocol, in the opinion of the investigator. Investigators should read and follow especially warning, contraindications, and precautions section of most recent Japan ixekizumab package insert (Taltz Subcutaneous Injection 80 mg syringe).
- [31] Have donated more than 400 ml of blood (for patients weighing ≥ 50 kg) or 200 ml of blood (for patients weighing < 50 kg) or plasmapheresis/platelet apheresis within 30 days prior to study entry, or plan to donate blood during the study.

- [32] Are women who are lactating or breastfeeding.
- [33] Are investigator site personnel directly affiliated with this study and/or their immediate families. Immediate family is defined as a spouse, parent, child, or sibling, whether biological or legally adopted.
- [34] Are Lilly employees or its designee or are employees of third-party organizations (TPOs) involved in the study.

